1.0 Introduction and Study Rationale

1.1 Overview

There is great need for improved pretreatment imaging in men with high-risk prostate cancer. We propose to develop an optimized simultaneous PET/MRI protocol for local, regional and whole body pre-therapeutic initial staging of high-risk prostate cancer in a single imaging session using the amino acid PET tracer, [¹⁸F]fluciclovine. This PET tracer has recently received FDA approval for use in biochemically recurrent prostate cancer, but its utility for staging prior to therapy and for monitoring response to therapy has not been established. Despite advances in the diagnosis and treatment of prostate cancer, the pretreatment staging of men with prostate carcinoma (PCa) is currently problematic. Conventional imaging is falsely negative for regional lymph node metastases in a substantial fraction of men. In particular, approximately 35% of men with high-risk prostate cancer will have biochemical recurrence even after optimal surgical resection. Therefore, we plan to examine patients at high risk for metastatic disease and who will predominantly be offered nonsurgical management of their prostate carcinoma. We will compare mpMRI alone to simultaneous fluciclovine-PET/MRI in terms of lesion detection in pelvic nodal stations. We will also correlate these imaging findings with established risk-prediction models to indirectly assess accuracy, as the vast majority of these patients will be managed non-operatively in this study. A second follow-up [¹⁸F]fluciclovine-PET/MRI study will be performed after completion of therapy. This repeat study after therapy will be used as part of a standard of truth (i.e. findings should resolve with effective therapy) and to generate preliminary data regarding the utility of fluciclovine-PET/MRI for assessing response to therapy.

If this preliminary study suggests a benefit of [¹⁸F]fluciclovine-PET/MRI in the pretreatment setting, additional larger studies will be designed based on these results. Because [¹⁸F]fluciclovine and PET/MRI are clinically available and FDA-approved for biochemically recurrent prostate cancer, this study has the potential for rapid and widespread impact. If [¹⁸F]fluciclovine-PET/MRI can reliably and accurately detect nodal metastases in high-risk prostate cancer patients, surgeons may use this new technology to decide if a high-risk prostate cancer patient is eligible for surgery, to extend the pelvic lymph node dissection to include suspicious lymph nodes identified by imaging, and for making decisions regarding initiating androgen-deprivation therapy. We will also generate preliminary data regarding the utility of [¹⁸F]fluciclovine-PET/MRI for assessing response to therapy.

1.2 Background and Rationale

Prostate cancer is a common malignancy with an estimated 180,890 new cases and 26,120 deaths in 2016.¹ Screening for prostate cancer is currently performed utilizing digital rectal exam and serum prostate specific antigen (PSA). Due to the high frequency of indolent prostate cancer, approximately 80% of cancers detected by screening are localized to the prostate. For these patients, the 5-year survival is nearly 100%.

However, there is a substantial minority of patients with high-risk prostate adenocarcinoma that are at significant risk for regional nodal and distant metastases at the time of diagnosis. In contrast to localized disease, the 5-year survival for patients with distant metastatic disease is 29%. Disease risk is stratified with the Gleason score on prostate biopsy, PSA, and clinical staging. These values provide estimated risks of organ-confined disease and extraprostatic disease based on established nomograms and Partin tables.² In these patients who undergo radical prostatectomy and bilateral pelvic lymph node dissection, approximately 30% experience biochemical recurrence. The 5-year disease-free survival rate drops from 85% of patients with no nodal metastases to 50% in those patients with nodal metastases. This is thought to be due to lack of detection of small volume metastatic disease not identified on conventional preoperative imaging. Because current imaging techniques have limited sensitivity for nodal metastases, many high-risk men are assumed to have metastatic disease and not offered potentially curative surgery. More accurate pretreatment staging has the potential to alter surgical planning or to prompt the earlier use of radiation or systemic therapy to decrease the risk of recurrence and improve survival. Through this study, we will generate key preliminary data assessing the ability of fluciclovine-PET coupled with simultaneous PET/MRI to improve the accuracy of pretreatment staging in men with high-risk prostate cancer.

While prostate MRI is valuable for the detection of occult primary lesions, its sensitivity and specificity for the detection of pelvic lymph node metastases is limited to RECIST criteria and nodal morphology. It is well known that normal-appearing lymph nodes on CT and MRI can harbor small volume metastatic disease not detected based on size and morphological criteria. Molecular imaging has great potential to supplement MRI and increase diagnostic accuracy, and simultaneous PET/MRI can provide both dedicated regional PET and MRI imaging for regional staging as well as whole body staging in a single imaging session.

Amino acid metabolism is upregulated by prostate cancer cells, with increased expression of the ASCT2 and LAT1 transporters. As a result, multiple amino acid analogues have been developed to image prostate cancer. Recently, the ¹⁸F-labeled amino acid *anti*-1-amino-3-[¹⁸F]fluorocyclobutane-1-carboxylic acid ([¹⁸F]FACBC, otherwise known as fluciclovine) received FDA approval for use in biochemically recurrent prostate cancer. Fluciclovine-PET/CT has been shown to be particularly effective for detecting nodal metastases and distant metastases in recurrent prostate cancer. Fluciclovine is a transport substrate for ASCT2 and to a lesser extent LAT1, but is not metabolized intracellularly or incorporated into proteins.^{3,4} A key advantage to the use of fluciclovine is minimal excretion of the radiotracer into the urine, which lends itself well to imaging the pelvis without the use of pre-scan urinary bladder catheterization. Studies with fluciclovine have focused primarily on biochemical recurrence using PET/CT. Currently, data are scarce regarding the role of fluciclovine in patients undergoing initial staging, and there are virtually no data using PET/MRI.⁵ A single study examining the effectiveness of fluciclovine PET/CT for detection of nodal metastases demonstrated increased detection of sub-centimeter pelvic lymph nodes when compared to conventional imaging.⁶

Several studies have examined the use of 2-deoxy-2-[¹⁸F]fluoro-D-glucose (FDG) PET/CT for the evaluation and staging of prostate cancer. FDG-PET/CT has not become a mainstay in the pretreatment staging of patients due to low sensitivity and specificity. In response, a number of radiotracers have been developed to detect metastatic disease in the setting of prostate cancer. The first alternative tracer in clinical use in the United States is [¹¹C]choline. Sensitivity for staging patients using [¹¹C]choline is higher than for FDG, but remains relatively poor with studies ranging from 45-73%.⁷⁻⁹ A significant logistical problem with the use of [¹¹C]choline is the 20 min half-life of the radiotracer, thus requiring on-site production by a cyclotron.

Prostate specific membrane antigen (PSMA) is a transmembrane cellular receptor that is overexpressed in prostate cancer cells. Recently, small molecules have been developed that bind to the extracellular component of the transmembrane PSMA receptor. These agents have been tagged with both ¹⁸F and ⁶⁸Ga for imaging and ⁹⁰Y and ¹⁷⁷Lu for therapeutic purposes. Restaging accuracy of fluciclovine and PSMA-PET/CT are superior to choline compounds, particularly at low PSA levels, although no direct comparison of PSMA ligands and fluciclovine PET are currently available in the published literature.¹⁰ A limitation of PSMA ligands is that approximately 10% of prostate carcinoma and nodal metastases are PSMA negative.¹¹⁻¹⁴ PSMA ligands are currently investigational in the United States and not available for routine clinical use.

While other PET tracers remain promising, [¹⁸F]fluciclovine has several key advantages. [¹⁸F]Fluciclovine is more widely available and can be distributed to centers without onsite radiolabeling capabilities due to its ¹⁸F-label. Initial data suggest that fluciclovine is diagnostically superior to [¹¹C]choline. Although PSMA ligands are promising, fluciclovine can have much greater near-term impact for pretreatment staging because it is FDA-approved. By accurately staging high-risk patients prior to treatment, we speculate that treatment algorithms can shift, allowing better assessment of surgical eligibility and therapy planning.

PET/MRI is likely the optimal modality to image patients for pretreatment staging of prostate carcinoma. In one study, a patient can undergo a multiparametric prostate MRI for characterization of the primary lesion and the extent of regional extraprostatic disease along with a molecular imaging study to improve the accuracy of regional staging and provide whole body staging. In addition, simultaneous acquisition of PET and MRI data allows for more accurate coregistration of MRI and PET data which may be difficult to achieve with software fusion, a key to detecting non-enlarged lymph nodes and other small lesions.

We will also develop preliminary data regarding the utility of fluciclovine-PET/MRI in early assessment of treatment response in this patient population. In men treated with radiation therapy and/or androgen deprivation therapy (ADT), early detection of treatment failure may identify patients who would benefit from additional local or intensive systemic therapy much sooner than is possible with serum PSA measurement alone. The favorable properties of PET/MRI are expected to be useful for early treatment response assessment as well. Because most of the patients in this study will not undergo

surgery, many of the post-therapy studies will be in men undergoing radiation therapy and/or androgen deprivation hormonal therapy. We will measure changes in fluciclovine uptake and MR parameters at a 3-6 month imaging time point and correlate these results with clinical follow up including progression-free survival. If fluciclovine-PET/MRI has utility for early assessment of response, men at high risk for recurrence based on imaging may be offered additional local therapy and/or systemic therapy prior to progression based on serum PSA measurements.

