2.0 Study Objectives

Specific Aim #1: Determine the concordance of imaging findings for fluciclovine-PET/MRI and mpMRI of the pelvis and prostate gland.

Hypothesis #1: Fluciclovine-PET/MRI will identify more regional lymph node metastases than mpMRI alone.

There have been numerous prior studies demonstrating the value of mpMRI for the locoregional staging for PCa. Prior studies in the setting of biochemical recurrence have demonstrated high sensitivity and specificity of fluciclovine-PET/CT for detection of recurrent disease in the prostate bed and extraprostatic disease.¹⁵ We expect the simultaneous acquisition of mpMRI and fluciclovine PET data to provide valuable preoperative staging information, with fluciclovine PET detecting metastatic disease in subcentimeter pelvic lymph nodes not identified with mpMRI alone. Additionally, fluciclovine-PET/MRI provides whole body staging in regions not evaluated by mpMRI and may detect additional distant metastases.

Specific Aim #2: Determine the correlation between organ-confined disease, lymph node metastases, extraprostatic extension, and seminal vesicle invasion on fluciclovine-PET/MRI with the expected frequencies of these metastases based on established nomograms and risk-prediction models as well as follow up fluciclovine-PET/MRI.

Hypothesis #2: Fluciclovine-PET/MRI will demonstrate metastases in the expected frequencies for patients with high-risk PCa and will regress with effective therapy.

For pretreatment patients with PCa, several clinical risk-predictors (including nomograms and Partin tables) utilize serum prostate-specific antigen (PSA), Gleason score, and clinical stage to predict organ-confined disease, the presence of extraprostatic extension, seminal vesicle invasion, and lymph node metastases.² Because majority of the high-risk prostate cancer population in this study will not undergo prostatectomy, nomograms and risk-prediction models combined with follow up fluciclovine-PET/MRI after therapy will be used as a surrogate for accuracy. If successful, this research plan will provide key data for further studies that will use histopathological confirmation as the reference standard.

Specific Aim #3: Measure changes in fluciclovine-PET/MRI at 6-12 weeks after initiation of therapy and correlate with serum PSA.

Hypothesis #3: Fluciclovine-PET/MRI parameters including fluciclovine uptake and fluciclovine-defined metabolic tumor volumes will change with effective therapy.

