Resolution of fluciclovine-PET/MRI findings after therapy will also be used to help confirm true lesions on the pre-treatment imaging. If successful, this research plan will provide key data for further studies in for initial staging and monitoring therapy response that will use histopathological confirmation and patient outcomes as the reference standards.

For the post-treatment imaging, a repeat fluciclovine-PET/MRI study will be performed at 6-12 weeks months after initiation of therapy. The fluciclovine-PET and MR measurements will be compared between the pre- and post-treatment studies. Early detection of men at high risk for early treatment failure might undergo additional treatment prior to PSA rise from nadir. In the small number of patients in this study who undergo prostatectomy, the follow up fluciclovine-PET/MRI has the potential to detect residual disease that could then be treated with additional local therapy.

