3.0 Investigational Plan

3.1 Study Design

- Prospective IRB-approved study enrolling patients with biopsy-proven high-risk prostate cancer for pretreatment fluciclovine-PET/MRI prior to the initiation of treatment and at three month follow-up
- All patients will undergo standard-of-care clinical evaluation and imaging workup with nuclear medicine bone scan and either CT of the abdomen and pelvis or MRI pelvis
- Majority of patients will be non-operative due to high-risk status, but participation in study does not exclude operative intervention
- Treatment team will initially be blinded to results of PET/MRI, but will be unblinded following standard-of-care imaging and formation of the initial treatment plan
- If study PET/MRI demonstrates a suspicious finding that may preclude a patient from operative intervention (in a patient being considered for surgery) or alter locoregional treatment (e.g. radiation therapy), the treatment team will be alerted to potentially investigate the finding further (i.e. additional imaging or biopsy)
- Findings on PET/MRI relayed to the clinical team may prompt further investigation on standard-of-care imaging and discussion in the genitourinary tumor board. If additional imaging and/or tumor board consensus indicates the need for biopsy, the biopsy can be billed to insurance as standard-of-care.
- A repeat fluciclovine-PET/MRI study will be performed at 6-12 weeks weeks after initiating therapy (typically radiation therapy, prostatectomy, and/or androgen deprivation therapy) at the time when serum PSA values are initially checked to establish response

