4.6 Imaging Information

4.6.1 $[^{18}\text{F}]$ Fluciclovine PET Preparation and Injection

The injected dose will be 370 MBq (10 mCi) of $[^{18}\text{F}]$ fluciclovine. The patient will be instructed to avoid strenuous exercise for 24 hours prior to injection and to avoid caloric intake for 4 hours prior to injection. PET/MRI imaging will begin immediately following injection. Intramuscular injection of glucagon 1 mg will be performed immediately prior to the prostate MRI portion of the PET/MRI.

4.6.2 $[^{18}\text{F}]$ Fluciclovine PET/MRI Protocol

Whole body imaging

Positron Emission Tomography Acquisition: The patient will be placed on the PET/MRI scanner in the supine position. Initial localizer images will be obtained. Dynamic images of the pelvis will be acquired for the first 8 min after fluciclovine injection with framing of 3 sec x 20, 10 sec x 12, 20 sec x 6, 180 sec x 1. Subsequently, static whole body images will be acquired from pelvis to skull base utilizing approximately eight 14 cm detector beds for 5 minute acquisitions per bed position. Correction for randoms, scatter, attenuation and reconstructions will be performed per the manufacturer's recommendations.

Whole Body MRI: Sequences performed will include MR attenuation correction (MRAC), axial and coronal T2 single shot fast spin echo, sagittal T1 turbo spin echo for skeletal evaluation, and whole body Dixon-derived sequences.

Following whole body PET imaging, a routine multiparametric MRI of the prostate gland will be performed at UAB in the PET/MRI scanner per institutional protocol, which includes high b-value diffusion-weighted imaging (b2000), small field-of-view T2 imaging, and dynamic contrast enhanced T1 images. An additional static pelvic PET acquisition will be performed concurrently.

Fluciclovine PET/MRI scans will be performed at two time points:

- Prior to initiation of treatment
- At 3-6 months following treatment initiation when routine clinical practice is to begin assessing PSA values for response

The study protocol has been submitted to, reviewed, and approved by the UAB Radiation Safety Committee.

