5.3 Exploratory Endpoints

- Use of [¹⁸F]fluciclovine PET/MRI at 3-6 months following initiation of treatment to evaluate response to therapy at the time when serum PSA is routinely checked following treatment initiation
- Correlate disease burden at 3 month follow up with serum PSA values
- Dynamic radiotracer uptake by the primary lesion and if this changes on the posttreatment [¹⁸F]fluciclovine-PET/MRI
- Changes in signal characteristics of primary intraprostatic lesion on posttreatment mpMRI
- Changes in initial treatment plan with added information provided by fluciclovine PET/MRI versus standard-of-care imaging alone

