6.4.2 Analysis for Secondary Endpoints and Specific Aim 2: Serum prostate-specific antigen (PSA) will be measured for each patient as a clinical risk-predictor as a validated measure to identify PCa and monitor response to treatment. Patients will be identified if they have PCa metastases and response to treatment determined by PSA level (expected) and by using [¹⁸F]fluciclovine PET/MRI (observed) at baseline and 3 months after treatment. To compare observed frequencies of metastases and expected frequencies, a McNemar test will be performed at baseline and 3 month after treatment separately. Further, a generalized estimation equation (GEE) method will be used to examine the association of two diagnosis methods accounting for correlation between baseline and 3 months measurements. Sensitivity, specificity, and accuracy of using [¹⁸F]fluciclovine PET/MRI will be estimated along with 95% CI. Due to the small sample size and potential for sparse data, we may use Firth's penalized likelihood approach. Data transfer, management, and analyses will be performed using Excel and SAS v9.4.

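### The follow-up scan is motivated by warning earlier than PSA, but no progression-free survival analysis is specified, and section 6.4.2 on its natural reading counts such a warning as a false positive

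*Combined protocol and SAP*

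**What the plan says.** **Purpose.** Section 1.2 says that in men given radiation and/or hormonal therapy, early detection of failure may identify those who would benefit from more treatment "much sooner than is possible with serum PSA measurement alone". The text under Aim 3 in section 2.0 repeats the idea: "Early detection of men at high risk for early treatment failure might undergo additional treatment prior to PSA rise from nadir". Section 1.2 also commits this study to measure change on the follow-up scan and to "correlate these results with clinical follow up including progression-free survival".

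**Comparator.** Aim 3 is to "Measure changes in fluciclovine-PET/MRI at 6-12 weeks after initiation of therapy and correlate with serum PSA". An exploratory endpoint in 5.3 is to "Correlate disease burden at 3 month follow up with serum PSA values". The scan is timed to the first response PSA: section 3.1 places it "at the time when serum PSA values are initially checked to establish response", and section 4.6.2 "At 3-6 months following treatment initiation when routine clinical practice is to begin assessing PSA values for response".

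**Analysis.** Section 6.4.2, headed as the analysis for secondary endpoints and Aim 2, identifies metastases and "response to treatment determined by PSA level (expected) and by using [¹⁸F]fluciclovine PET/MRI (observed) at baseline and 3 months after treatment". It applies a McNemar test at each time point and a GEE model across both, then estimates sensitivity, specificity and accuracy of PET/MRI with 95% confidence intervals.

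**Follow-up.** Section 3.7 allots 12 months to enrolment and imaging. Section 4.6.5, on patient follow-up, deals with possible side effects of the tracer. The text under Aim 3 leaves patient outcomes as a reference standard to further studies.

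**The concern.** A test meant to give earlier warning than PSA has to be judged against something that happens later than the PSA it is compared with. The plan names such an outcome once, in the background, and does not carry it into the endpoints or the analysis. What remains for response is agreement with PSA at about the time of the scan.

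The man of most interest to the rationale has persistent uptake while his PSA is still responding, and progresses later. With PSA as the standard for response, he is indistinguishable from a man whose scan is simply wrong. The best result PET/MRI can then achieve is to match a PSA value already in hand. At stake is whether the pilot can give even preliminary support to the earlier-warning idea, and whether the accuracy figures from 6.4.2 would mislead whoever designs the next study.

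**Working it through.** **1. The plan's own figure.** The only computed statistical figures are the Clopper-Pearson intervals in section 6.2, for n = 15. With x = 15p, lower limit = 2.5% quantile of Beta(x, n − x + 1) and upper limit = 97.5% quantile of Beta(x + 1, n − x):

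| p | x | 95% CI, recomputed | 95% CI, section 6.2 |
|---|---|---|---|
| 20% | 3 | 4.3 to 48.1 | 4.3 to 48.1 |
| 25% | 3.75 | 6.9 to 53.4 | 6.9 to 53.4 |
| 30% | 4.5 | 9.7 to 58.4 | 9.7 to 58.4 |

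They reproduce, but they concern detection of metastasis. Nothing numerical is stated for response or PFS.

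**2. Tracing PFS through the plan.**

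| Place | PFS or progression outcome? |
|---|---|
| 1.2 Background | Yes, as something this study will do |
| 2.0 Aim 3 | No; comparator is PSA, and patient outcomes are left to later studies |
| 5.1, 5.2, 5.3 Endpoints | No |
| 6.4, 6.4.1, 6.4.2 Analysis | No |
| 3.7 Duration, 4.6.5 Follow-up | No outcome follow-up period or schedule |

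**3. Which reference the accuracy figures use.** Section 6.4.2 names none outright. Within it, PSA is the expected classification and PET/MRI the observed one. Elsewhere, section 2.0 gives nomograms plus the follow-up scan as the surrogate for accuracy. The nomograms are described there for pretreatment patients, so they cannot classify response, and the follow-up scan cannot be the reference for its own response reading. For response, PSA is the only candidate left.

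**4. Effect per man.** Let N men be PSA responders and k of them PET-positive at follow-up. With PSA as reference:

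- apparent specificity = (N − k)/N, so each such man costs 1/N;
- N = 15: 1/15 = 6.7 points; N = 10: 1/10 = 10.0 points;
- apparent accuracy over all 15 men falls by 1/15 = 6.7 points per man.

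The range N = 10 to 15 is an assumption; the plan gives no expected PSA response rate and no figure for k. The direction does not depend on either: a PET-positive result in a PSA responder never raises specificity or accuracy.

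**5. An extreme illustration.** Sections 1.1 and 1.2 give biochemical recurrence of about 35% and 30% after surgery: 0.30 × 15 = 4.5 and 0.35 × 15 = 5.25, say 5 men. Suppose the scan is perfect against later progression.

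| Later failures | Already PSA-positive at scan | Apparent specificity (95% CI) | Apparent accuracy |
|---|---|---|---|
| 5 | 0 | 10/15 = 66.7% (38.4 to 88.2) | 10/15 = 66.7% |
| 5 | 2 | 10/13 = 76.9% (46.2 to 95.0) | 12/15 = 80.0% |
| 2 | 0 | 13/15 = 86.7% | 13/15 = 86.7% |
| 6 | 0 | 9/15 = 60.0% | 9/15 = 60.0% |

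Where no man is PSA-positive, sensitivity is undefined (0/0). Against later progression the same scans would score 100% on both measures. This shows the mechanism and does not forecast the result.

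**The case against.** Much can be said for the plan.

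- **Section 6.4.2 does not state that PSA is the accuracy reference.** It defines neither a PSA response rule nor a PET response rule. McNemar is symmetric and calls neither method wrong. A reader might infer that the plan expressly scores early detection as an error; the text does not say so. The false-positive reading rests on the expected and observed labels and on the absence of any other reference for response. This stands as a limit on the wording.
- **Aim 3 and 5.3 specify correlation only, with PSA values that are not dated.** Only 6.4.2 clearly pairs scan and PSA at 3 months. This stands, and it confines the accuracy problem to 6.4.2.
- **A reader might infer that progression data will never be collected, so that 0 of 15 men could contribute.** The documents do not support that. Section 3.7 limits enrolment and imaging, not outcome follow-up, and section 4.6.5 does not exclude chart review. What can be said is that collection is not specified.
- **Earlier warning than PSA is rationale, not a tested hypothesis.** Hypothesis 3 is only that uptake and metabolic volume change with effective therapy, and patient outcomes are deferred to later studies. This stands, but the deferral conflicts with the commitment in 1.2; one of them has to change.
- **The study is a descriptive pilot of 15 men with no decision rule on response.** This limits the consequence. It does not remove the problem, because 6.4.2 places the PSA comparison under secondary endpoints and asks for accuracy figures with intervals.

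**Conclusion.** The concern holds in this form. Section 1.2 commits the study to correlating follow-up scan changes with PFS, and the plan specifies no endpoint, definition, follow-up period or analysis to do it. Section 6.4.2, on its natural reading, makes 3-month PSA the standard for response, so a scan that detects failure before PSA can only lose apparent accuracy: about 7 to 10 points of specificity per such man if 10 to 15 men are PSA responders.

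A reader might go on to infer that about 5 men would be misclassified and specificity pulled down to about 67%. The documents do not support that as an estimate. The 30 to 35% recurrence figures are for operated men and carry no time horizon, most men here will not have surgery, and the illustration assumes a perfect scan with no failure yet visible on PSA. The number of men affected is unknown.

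This should be corrected, but it does not threaten the primary aim, which concerns concordance of PET/MRI with mpMRI.

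**What to change.** **In 6.4.2:** report the 3-month PET/MRI and PSA comparison as concordance or correlation only. Do not use same-time PSA as the reference for sensitivity, specificity or accuracy of response.

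**Then choose one:**

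- **(a)** Add to 5.3 and Aim 3 an exploratory, descriptive outcome abstracted from routine records: PSA values and date of progression, under a definition stated in advance, to a fixed date after each man's second scan. Describe PET/MRI change against it. Record any treatment change prompted by the PET/MRI, since this could alter the later outcome. Section 6.6 says all patient data will be anonymised, so a linkage key has to be kept.
- **(b)** Delete the PFS and earlier-than-PSA statements from 1.2 and Aim 3.

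**Under either option:** reconcile the timing of the second scan, given as 6-12 weeks (Aim 3, 3.1), three months (3.1, 5.3, 6.4.2) and 3-6 months (1.2, 4.6.2, 5.3). The PSA comparison cannot be dated until these agree.

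**Cost.** Both options need a protocol amendment with IRB approval (6.5.4). Option (a) adds chart review of 15 men, a later lock for this one exploratory analysis and possibly a consent line, with no extra visits or tests. Few progression events should be expected, so the result would be descriptive only. Option (b) costs wording alone, but gives up the earlier-warning question in this study.
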